The current focus of U.S. antimicrobial stewardship efforts has been to establish local hospital programs outfitted with a multi-disciplinary team of clinicians and pharmacists. National recommendations involve reviewing the antimicrobial formulary, and ensuring appropriate weight-based dosing, and IV vs oral selection. In recent years, national recommendations have targeted clinical care optimization by recommending processes to establish and update local antibiograms, evidence-based treatment guidelines and order sets, and active review of antimicrobial therapy to narrow antibiotic choice when pathogens grow from clinical cultures – e.g. “de-escalation” after when clinical cultures yield pathogens, generally three to seven days after cultures are sent.

These efforts, while admirable, do not address the majority of inappropriate antibiotic use in hospital settings, because the majority of antibiotics are prescribed empirically while pending any possible knowledge of the causative pathogen from clinical cultures. Culture results and antibiotic susceptibilities typically become available at or after the third hospital day, which is also the median duration of hospital stays. Therefore, the target for de-escalation is modest, compared to the substantial use of empiric therapy, which is often initiated in emergency rooms.

Analysis of the Need and Impact on Healthcare

Abdominal (ABD) infections are among the most common infectious reasons for hospitalization. ABD infections are responsible for over a million hospitalizations each year and HCA Healthcare data from 140 hospitals suggest that over 80% of ABD infections are treated with an empiric regimen that includes an extended-spectrum antibiotic intended to treat MRSA, *Pseudomonas*, or multidrug-resistant *Enterobacteriales*. Nevertheless, estimates of the frequency of these pathogens is only 2%; thus, showcasing the inordinate unnecessary use of extended-spectrum antibiotics.

While there is an appropriate focus on rapid initiation of extended-spectrum antibiotics for patients who are septic or require critical care, there is a need to focus on use of standard spectrum empiric antibiotic regimens for the much larger population of patients who require hospitalization, but are not critically ill, and who are at low risk of MDR pathogens.

B.2.1 Innovations in Implementation

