The primary trial outcome is defined as the summed number of different ES antibiotics received during each empiric day. An empiric day is a day within the first three days of an admission. We define this outcome as the Total Empiric Extended-Spectrum Days of Therapy (ES-DOT). For clarity, the calculation is as follows: we define a DOT for a particular ES antibiotic as a day in which any number of doses of that antibiotic is given. Different ES antibiotics are summed within each empiric day for each patient admission to determine DOT in that at-risk day. Antibiotics given during an associated emergency department visit on the date of hospital admission are counted toward the ES-DOT of the first hospital day.

The main trial results will be based upon as-randomized, unadjusted analyses of admission-level ES-DOT. In contrast to the national DOT measure defined by CDC for hospitals, we define ES-DOT at the individual admission level so that we can perform analyses on individuals.

The trial will be assessed among the cohort of adult admissions who: 1) have administrative claims codes indicating an abdominal infection is present on admission; 2) received any antibiotic within 3 days of admission; and 3) were admitted to a non-ICU location. For admissions initially on a non-ICU floor and transferred to the ICU, analysis will include only admission days on the non-ICU floor within 3 days of admission.

The trial periods are defined as follows: (1) Baseline: January 1, 2019 – December 31, 2019 (12 months); (2) Phase-in: August 2, 2022 – December 31, 2022 (5 months, does not contribute to analysis); (3) Intervention: January 1, 2023 – December 30, 2023 (12 months). The main evaluation of all outcomes will be difference-in-difference between the Intervention and Baseline periods and between study arm. Trial analysis will use a baseline period prior to the arrival of the COVID-19 pandemic since hospital operations and case mix were severely impacted by this pandemic between Winter 2020-Spring, 2022.²⁵⁻²⁹ Although at the time of this

writing (June, 2022), COVID-19 surges continue to occur nationally, clinical operations and patient case mix at most hospitals have largely returned to near pre-pandemic activity in the setting of widespread vaccination and milder virus strains. Phase-In is scheduled for August, 2022 as participating hospitals are in a state of recovery sufficient to launch the trial intervention with pharmacy/physician engagement.

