Subsequent analyses of the primary and secondary outcomes will include both as-treated and adjusted models. Adjusted models will account for individual characteristics such as age, gender, comorbidities, and prior history of MDROs as well as hospital characteristics such as hospital antibiotic resistance. We will also account for seasonality. All adjusters will be determined a priori. These analyses will be reported as point estimates with confidence intervals and without p-values. The reason for including these analyses is to provide additional information related to the trial outcomes for readers to assess the effects of potential confounders. The reason to not include them in a formal multiple comparisons adjustment is because these analyses are non-independent evaluations relative to the as-randomized unadjusted analyses.

We will separately evaluate intervention period effects by arm alone.

Safety Outcomes

Safety outcomes noted in the above table will be assessed in the most conservative manner to identify potential safety issues. Safety outcomes are required because a reduction in ES-DOT might be achieved only by incorrectly withholding ES antibiotics when they were really needed. Each safety outcome will be evaluated for non-inferiority using an as-randomized unadjusted analysis with a one-tailed significance set at alpha = 0.05. Length-of-stay and days to ICU transfer are evaluated within 14 days of admission since empiric antibiotic selection within the first 3 hospital days is not expected to be a main driver of either outcome beyond this time period; evaluation of baseline data also shows that 93% of abdominal patients have length-of-stay equal to or less than 14 days. Analyses planned for these assessments are proportional hazards models with random effects for each hospital and admission. These models are sometimes called frailty or shared frailty models. Because these are safety outcomes, we do not intend to make adjustments for multiple comparisons in testing them, further increasing conservatism.

All analyses will be performed using current versions of SAS (Version 9.4, as of writing, SAS Institute, Cary NC) and/or R (Version 4.0, as of writing).

C.2.11 Power Size/Sample Size Calculations

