Power assessment proceeded as follows, using a Monte Carlo approach.²⁵ We used available data to define a baseline period of 1/1/2019-12/31/2019. In a bootstrap procedure, individuals were selected with replacement from within each hospital, once to represent baseline data and separately to represent “intervention period” data. Hospitals were then “randomized” to intervention or control according to multiple parameters, including number of admissions with abdominal infection and ES-DOT. We then modified the outcomes for the bootstrapped individuals in the “intervention” period in the “intervention” arm to reflect the effect of the intervention.²⁹

We assessed power to identify an overall 12.5% relative reduction in ES-DOT. This effect was implemented by reducing the relative empiric days of therapy for each admission which was exposed to the CPOE prompt. The amount of reduction was a uniform random variate between 0.75 and 1. For example, if the bootstrapped patient initially received 8 ES-DOT and was assigned to have a 12.5% reduction, then that admission intervention ES-DOT would be reduced to 7 days ($8*0.875=7$). The reduction of ES-DOT was selected with a lower bound determined by the investigators as the minimal effect achieved that would be clinically meaningful. Using this method, we have $\geq 99.9\%$ (99.6-99.9%) power to detect this effect.

Since adoption of the intervention will be heavily influenced by the ability to demonstrate safety, our study size was based on the power to detect non-inferiority for safety outcomes. We used methods similar to the above to calculate the power to identify at least a one day increase in length-of-stay for 12.5% of patients who had hospitalizations less than 14 days and found the power was 91.5% (CI 89.6-93.2%), where non-inferiority is defined as a hazard ratio no smaller than 0.98. For days to ICU transfer, we estimated the power to detect a 2% increase in transfers to the ICU on hospital day 3 through 14 to be $>99.9\%$ (CI 99.6-99.9%), where non-inferiority is defined as having a hazard ratio no greater than 1.1 (fewer days to ICU results in a hazard ratio above 1).

For completeness, we note that there are other pre-specified outcomes intended for exploratory analysis in secondary papers for the INSPIRE ABD trial in Table 4 below.

Table 4: Secondary Manuscripts - Other Pre-Specified Outcomes

Secondary Manuscripts (other pre-specified secondary exploratory analyses for later manuscripts)	

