The primary trial analysis will use an as-randomized unadjusted model with two-tailed significance set at alpha = 0.05. Secondary outcomes will be assessed using an as-randomized unadjusted model and will include adjustment for multiple comparisons with two-tailed significance set at alpha = 0.025 for the two secondary outcomes.

Subsequent analyses of the primary and secondary outcomes will include both as-treated and adjusted models. Adjusted models will account for individual characteristics such as age, gender, comorbidities, and prior history of MDROs as well as hospital characteristics such as hospital antibiotic resistance. We will also account for seasonality. All adjusters will be determined a priori. These analyses will be reported as point estimates with confidence intervals and without p-values. The reason for including these analyses is to provide additional

information related to the trial outcomes for readers to assess the effects of potential confounders. The reason to not include them in a formal multiple comparisons adjustment is because these analyses are non-independent evaluations relative to the as-randomized unadjusted analyses.

Safety Outcomes

Safety outcomes are required because a reduction in ES-DOT might be achieved only by incorrectly withholding ES antibiotics when they were necessary. Each safety outcome will be evaluated for non-inferiority using an as-randomized unadjusted analysis with a one-tailed significance set at alpha = 0.05. For length of stay, the non-inferiority margin is a hazard ratio of 0.98. For days to ICU transfer, the non-inferiority margin is a hazard ratio of 1.1 (fewer days to ICU results in a hazard ratio above 1). Analyses planned for these assessments are proportional hazards models with random effects for each time period, hospital, and admission. These models are sometimes called frailty or shared frailty models. Because these are safety outcomes, we do not intend to make adjustments for multiple comparisons in testing them, further increasing conservatism. As above, it may not be possible to include multiple admissions.

All analyses will be performed using current versions of SAS/STAT and/or R packages lme4 and coxme, unless better packages become available in the meantime.

Further Planned Analyses

We note that there are other pre-specified outcomes intended for exploratory analysis in secondary papers for the INSPIRE ABD trial in Table 5 below.

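### The >99.9% power quoted for ICU transfer is not the power of the planned non-inferiority test unless ICU transfers are very common

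*Protocol*

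**What the plan says.** Protocol section C.2.11 (Power Size/Sample Size Calculations) states that "our study size was based on the power to detect non-inferiority for safety outcomes". For ICU transfer it then reports that "we estimated the power to detect a 2% increase in transfers to the ICU on hospital day 3 through 14 to be" more than 99.9% (CI 99.6-99.9%). The same sentence adds the HR margin of 1.1 as the definition of non-inferiority. It does not say whether 2% is relative or absolute, what HR was simulated, what the baseline transfer rate was, or which simulated result counted as success.

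The test itself is set elsewhere. Protocol section H.3: "Each safety outcome will be evaluated for non-inferiority using an as-randomized unadjusted analysis with a one-tailed significance set at alpha = 0.05". SAP, Safety Outcomes: "For days to ICU transfer, the non-inferiority margin is a hazard ratio of 1.1". The contrast is in Protocol section H.3: "The main evaluation of all outcomes will be difference-in-difference between the Intervention and Baseline periods and between study arm"; the SAP's Primary Statistical Analysis section says the same. The SAP contains no power statement that would replace the protocol's.

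**The concern.** Power to detect an increase and power to rule out an increase beyond a margin are different quantities. The first is the chance of rejecting equality when harm is present. The second is the chance of passing the non-inferiority test when the intervention is safe, or nearly so. The section announces the second, words the ICU figure as the first, and attaches the non-inferiority margin to it.

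Section C.2.11 also says that adoption will depend heavily on showing safety, and ICU transfer is one of only two safety outcomes. A reader who believes that a safe intervention would pass more than 99.9% of the time could take a failed ICU test as strong evidence of harm. That inference is sound only if the figure belongs to the planned test.

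**Working it through.** **Inputs from the documents.** Margin HR 1.1 and one-sided 0.05 (Protocol H.3 and C.2.11; SAP Safety Outcomes). Difference-in-differences (Protocol H.3). About 99,000 patients in the 12-month intervention period, 46 against 46 hospital units (Protocol, Brief Overview).

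**Assumptions.** A baseline year of equal size, hence 49,500 admissions in each of four arm-period cells; equal events per cell; no clustering, which favours the plan; ICU-transfer rate for days 3-14 varied from 1% to 10%, because the documents give none.

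**Formulas.** With d events per cell, SE(log HR) = sqrt(4/d) for difference-in-differences and sqrt(2/d) for the intervention year alone.
- Non-inferiority power = Phi((ln 1.1 - ln HR)/SE - 1.645), where ln 1.1 = 0.0953.
- Power to detect harm = Phi(ln HR/SE - 1.645).

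**Step 1: can >99.9% be reached if 2% is relative?** True HR 1.02 and ln 1.02 = 0.0198, so the distance to the margin is 0.0755.
- d = 4 × ((1.645 + 3.090)/0.0755)² ≈ 15,730 per cell, and 15,730/49,500 = 32%. Intervention year alone: 7,865, or 16%.
- At true HR 1.00: d = 4 × (4.735/0.0953)² ≈ 9,873 per cell, or 20%. Intervention year alone: 4,936, or 10%.
- Read instead as power to detect HR 1.02, the result is only 8-13% at rates of 1-5%.

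**Step 2: can it be reached if 2% is absolute?** Two added points give an HR of about 3.0, 2.0, 1.4 and 1.2 at base rates of 1, 2, 5 and 10%. As a simple ratio, 1 + 0.02/r exceeds 1.1 whenever r is below 20%. At r = 10%, d = 4,950, SE = 0.0284 and ln 1.21 = 0.19:
- power to detect harm = Phi(0.19/0.0284 - 1.645), above 99.9%;
- non-inferiority power = Phi((0.0953 - 0.19)/0.0284 - 1.645), essentially zero.

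At 1-5% the pattern is the same. Of the readings tried at rates of 1-10%, only power to detect a two-point harm gives the stated value under difference-in-differences. The lower confidence limit of 99.6% agrees with 1,000 rejections in 1,000 simulations (0.025^(1/1000) = 0.9963), but does not show which hypothesis was being rejected.

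**Step 3: power of the planned test at true HR 1.00.** Example at 5%: d = 2,475, SE = 0.0402, Phi(0.0953/0.0402 - 1.645) = Phi(0.73) = 77%.

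| ICU-transfer rate | 1% | 2% | 3% | 5% | 8% | 10% |
|---|---|---|---|---|---|---|
| Difference-in-differences, 49,500 per cell | 28% | 44% | 58% | 77% | 91% | 96% |
| Same, true HR 1.02 | 21% | 32% | 43% | 59% | 77% | 84% |
| Difference-in-differences, 30,000 per cell | 21% | 32% | 42% | 58% | 76% | 83% |
| Intervention year only, 49,500 per arm | 44% | 68% | 83% | 96% | 99.5% | 99.9% |

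The 30,000 row reflects the Protocol Summary, which in one place gives about 60,000 patients. With 49,500 per cell, 80% power at HR 1.00 needs about 2,723 transfers per cell (5.5%).

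**Clustering.** A between-unit SD of 0.1 in the period change of the log hazard adds 2 × 0.1²/46 = 0.00043 to the variance and lowers the 5% value from 77% to 68%.

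**The case against.** Four points can be made for the plan.

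- **The sentence says what it says.** It speaks of detecting a 2% increase, and as power to detect a two-point harm the number may be computed correctly. That stands, and no miscalculation is shown. But the figure is offered as support for a study size based on non-inferiority, and for that purpose it is the wrong quantity.
- **High transfer rates would rescue it.** At the lower limit of the stated interval, 99.6% power at HR 1.02 needs a rate of about 26%, or 13% in a single-period comparison. No passage excludes such rates, so the point has to carry that condition.
- **The contrast is not fully written out for the safety models.** The SAP describes "proportional hazards models with random effects for each time period, hospital, and admission" without stating an arm-by-period term, and Protocol section H.3 also plans a look at the intervention period by arm alone. Difference-in-differences for all outcomes is still the better reading. The single-period figures are given for this reason, and they too need a rate of 10-16% for 99.9%.
- **It is late.** The SAP is dated after the intervention year, so revised power cannot alter study size, and low power does not create a false claim of safety. Both are true; what remains at stake is how the ICU result is read.

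A reader might go further and infer that the ICU test is badly underpowered and that a safe intervention would probably fail. The documents do not support this. Without a transfer rate the event count is unknown, and power is 91-96% at rates of 8-10%. Section B.2 of the protocol places culture results "at or after the third hospital day, which is also the median duration of hospital stays", but that is a general remark about hospital stays, not a statistic for this cohort, and does not establish a low transfer rate.

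**Conclusion.** The concern holds as a mismatch between the stated power and the planned test. Under a relative reading, >99.9% requires about 32% of admissions to go to the ICU on days 3-14 (16% in a single-period comparison); even at true HR 1.00 it requires 20% (10%). Under an absolute reading, the simulated effect lies beyond the margin at any base rate below about 20%, so the figure is power to detect harm and not power to show safety.

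The actual power cannot be fixed from the documents. The range of 28% to 96% for rates of 1% to 10% assumes 99,000 admissions in each period, true HR 1.00, difference-in-differences and no clustering. It would be lower with 60,000 patients or with hospital-by-period variation, and higher for a single-period contrast.

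**What to change.** Replace the ICU sentence in section C.2.11, re-running the existing bootstrap on the 2019 data. The new text should give:

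- the 2019 ICU-transfer rate for hospital days 3-14;
- whether 2% is relative or absolute, and the HR that it implies;
- the power to meet HR below 1.1 at true HR 1.00 and at any tolerated increase, under the planned contrast and one-sided 0.05;
- the number of admissions used, since the protocol gives both 99,000 and 60,000;
- power to detect harm, if wanted, as a separate figure under that name.

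The cost is one re-run and a rewritten paragraph. No extra patients are needed, and the margin and test stay as they are. The downside is that the stated power may be less favourable.

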The INSPIRE-ASP Trial (INtelligent Stewardship Prompts to Improve Real-time Empiric Antibiotic Selection for Patients) for Abdominal (ABD) Infections Statistical Analysis Plan

NCT:05423743

3/29/2024

(INtelligent Stewardship Prompts to Improve Real-time Empiric Antibiotic Selection for Patients)

Statistical Analytic Plan, 3/29/2024

[name]

Background

The **INSPIRE Abdominal Infections Trial** (INtelligent Stewardship Prompts to Improve Real-time Empiric Antibiotic Selection for Patients with Abdominal Infections) is a cluster-randomized trial of HCA Healthcare (HCA) affiliated hospitals to determine whether antibiotic prescribing practice for adult hospitalized patients admitted to non-critical care units with abdominal (ABD) infections can be affected by providing physicians with individualized risk estimates for whether a patient with an abdominal infection is likely to have an antibiotic-resistant infection. It compares routine care to a real-time smart prompt to use a standard-spectrum antibiotics when a physician orders an extended-spectrum antibiotic (ES) for a patient whose risk of antibiotic resistant infection is low (<10%). The main goal is to see if there is a difference in the empiric antibiotic prescribing practices for ES. The term “antibiotics” refers to antibacterial antibiotics in this trial. We define antibiotics administered during the first three days of hospitalization as empiric treatment because infecting pathogens and their antimicrobial susceptibilities are typically not known during this period. We refer to these first three days as the empiric period.

Extended-spectrum antibiotics are defined in Table 1 below.

Table 1: Extended-Spectrum Antibiotics in the INSPIRE-ASP Abdominal Infections Trial

Category	Extended-Spectrum Antibiotics for INSPIRE CPOE Alerts
Anti-MRSA	Ceftaroline, Daptomycin, Linezolid ¹ , Vancomycin ²
Anti-VRE	Daptomycin, Linezolid ¹ , Tigecycline
Anti-Pseudomonals	Aztreonam, Cefepime, Ceftazidime, Piperacillin/tazobactam
Anti-ESBL	Ertapenem, Imipenem, Meropenem, Ceftolozane/tazobactam
Anti-CRE	Ceftazidime/avibactam, Imipenem/relebactam, Meropenem/vaborbactam, Polymixin B, Colistin, Tigecycline

¹Both oral and intravenous (IV) formulations

²IV formulation only

Note: Does not include aminoglycosides or fluoroquinolones.

Abbreviations: **MRSA** - Methicillin Resistant *Staphylococcus aureus*; **VRE** – Vancomycin Resistant *Enterococci*; **ESBL** – Extended Spectrum Beta Lactamase producer; **CRE** – Carbapenem Resistant Enterobacteriaceae

Participating hospitals are randomized to:

- **Arm 1 – Routine Care**
- **Arm 2 – Real-Time Risk Estimation Smart Prompt**

Computerized physician order entry (CPOE) prompt that recommends standard-spectrum

antibiotics in patients admitted for ABD infections who are prescribed extended-spectrum antibiotics and calculated to have low risk (<10%) for an antibiotic resistant infection.

Trial Outcomes

Table 2: Primary and Secondary INSPIRE-ASP Abdominal Infections Trial Outcomes

Outcome	Metric
Primary Trial Outcome	
Total Empiric Extended-Spectrum Antibiotic Days of Therapy (ES-DOT)	The number of different extended-spectrum antibiotics received by the patient each empiric day, summed across the first 3 days of hospitalization. ¹
Secondary Trial Outcomes	
Vancomycin Days of Therapy per Empiric Day	The number of days Vancomycin was received by the patient on the first 3 days of hospitalization. ¹
Total Empiric Antipseudomonal Antibiotic Days of Therapy	The number of different antipseudomonal antibiotics received by the patient each empiric day, summed across the first 3 days of hospitalization. ¹

¹E.g., if a patient is admitted for 2 days, ES-DOT will be calculated across those 2 days; however if a patient is admitted for 4 days, only the first 3 days will be evaluated.

Safety outcomes planned for the primary manuscript are shown in Table 3. Length of stay and days to ICU transfer are evaluated within 14 days of admission since empiric antibiotic selection within the first 3 hospital days is not expected to be the main driver of either outcome beyond this time; evaluation of baseline data also shows that 93% of abdominal patients have length-of-stay equal to or less than 14 days.

Table 3: Other Pre-Specified Outcomes – Trial Safety Outcomes

Safety Trial Outcomes (other pre-specified outcomes)	
ICU Transfer [Safety Outcome]	Days to ICU transfer, between hospital days ≥ 3 and ≤ 14 .
Length-of-stay [Safety Outcome]	Days from hospital admission until discharge or hospital day 14, whichever comes first, where admission day is hospital day 1.

Data Collection Details

The trial will be assessed among the cohort of adult admissions who: 1) have administrative claims codes indicating an abdominal infection is present on admission; 2) received any antibiotic within 3 days of admission; and 3) were admitted to a non-ICU location.

The rationale for including only the first three days of the admission is that this is when the actual status of the patient with respect to the need for an ES antibiotic is unknown. Bearing this in mind, antibiotics given during an associated emergency department visit on the date of hospital admission are counted toward the ES-DOT of the first hospital day.

The trial baseline period includes January 1, 2019 – December 31, 2019 (12 months). The intervention period includes January 1, 2023 – December 31, 2023 (12 months). The baseline was selected to include time prior to the arrival of the COVID-19 pandemic since hospital operations and case mix were dramatically affected between Winter 2020-Spring, 2022.¹⁻⁴ Although COVID-19 surges have continued to occur, clinical operations and patient case mix at most hospitals have largely returned to near pre-pandemic activity. We considered that a state of pre-pandemic normalcy returned by summer of 2022, and introduced our intervention on August 2, 2022. The period between then and December 31, 2022 is considered a phase-in period and is not used in trial evaluation.

Primary Statistical Analysis

The primary trial outcome is defined as the summed number of different ES antibiotics received during each empiric day, on the patient-admission level. An empiric day is a day within the first three days of an admission. We define this outcome as the Total Empiric Extended-Spectrum Days of Therapy (ES-DOT). For clarity, the calculation is as follows: we define a DOT for a particular ES antibiotic as a day in which any number of doses of that antibiotic is given. Different ES antibiotics are summed within each empiric day for each patient admission to determine DOT in that at-risk day.

The main trial results will be based upon as-randomized, unadjusted analyses of admission-level ES-DOT. We note that the national DOT measure defined by CDC is measured at the hospital level. We define ES-DOT at the individual admission level so that we can perform analyses on individuals.

The main evaluation of all outcomes will be based on the difference in differences between the intervention and baseline periods and between study arms.

The unit of analysis will be individual admissions. Individual patients can contribute more than one admission. The analytic model will be a generalized linear mixed effects model for differences in differences, with random effects to account for correlation within hospital between period, within hospital within period between patient, and within patient between admission. We plan to use a Poisson model for analysis of outcomes as follows:

$$\log(y_{ijph}) = \beta_0 + \beta_1 A_{ijph} + \beta_2 T_{ijph} + \beta_3 A_{ijph} T_{ijph} + b_{0h} + b_{1h} T_{ijph} + g_j + \log(ed_j)$$

where y_{ijph} is the ES-DOT for patient i for admission j in period p at hospital h , and $A_{ijph} = 1$ if hospital h is in the intervention arm and 0 if not, and $T_{ijph} = 1$ if p is the intervention period and 0 if baseline period. The random effects b_{0h} and b_{1h} allow for different baseline mean admission-level ES-DOT for each hospital and each hospital in the intervention period, respectively. Equivalently, they allow for correlation within hospital at different levels at baseline and at follow-up. The random effect g_j allows each patient to have a different mean ES-DOT. Finally, ed_j is the number of empiric days in the admission. We note that it may not be possible to fit models with the g_j parameter, for various numerical and computational reasons—the most prominent being a relative sparsity of patients with readmissions. If that proves to be the case, we will randomly select one admission per patient and use the model above without that parameter and omitting the j subscript.

The assessment of trial success will be determined by assessing the significance of the arm by period interaction term β_3 , which estimates the log relative rate of the outcome due to being in the intervention arm in the intervention period. The exponentiated parameter estimate for β_3 is the estimated relative rate of ES-DOT per at-risk day due to the intervention, relative to the baseline period. For example, if β_3 had a negative value and a p-value <0.05 , we would conclude that the patient-specific CPOE smart prompts generated a benefit over routine care. Exponentiating the parameter value would provide an estimate of the relative reduction due to the intervention in the expected ES-DOT per at-risk day.

The primary trial analysis will use an as-randomized unadjusted model with two-tailed significance set at alpha = 0.05. Secondary outcomes will be assessed using an as-randomized unadjusted model and will include adjustment for multiple comparisons with two-tailed significance set at alpha = 0.025 for the two secondary outcomes.

Subsequent analyses of the primary and secondary outcomes will include both as-treated and adjusted models. Adjusted models will account for individual characteristics such as age, gender, comorbidities, and prior history of MDROs as well as hospital characteristics such as hospital antibiotic resistance. We will also account for seasonality. All adjusters will be determined a priori. These analyses will be reported as point estimates with confidence intervals and without p-values. The reason for including these analyses is to provide additional

information related to the trial outcomes for readers to assess the effects of potential confounders. The reason to not include them in a formal multiple comparisons adjustment is because these analyses are non-independent evaluations relative to the as-randomized unadjusted analyses.

Safety Outcomes

Safety outcomes are required because a reduction in ES-DOT might be achieved only by incorrectly withholding ES antibiotics when they were necessary. Each safety outcome will be evaluated for non-inferiority using an as-randomized unadjusted analysis with a one-tailed significance set at alpha = 0.05. For length of stay, the non-inferiority margin is a hazard ratio of 0.98. For days to ICU transfer, the non-inferiority margin is a hazard ratio of 1.1 (fewer days to ICU results in a hazard ratio above 1). Analyses planned for these assessments are proportional hazards models with random effects for each time period, hospital, and admission. These models are sometimes called frailty or shared frailty models. Because these are safety outcomes, we do not intend to make adjustments for multiple comparisons in testing them, further increasing conservatism. As above, it may not be possible to include multiple admissions.

All analyses will be performed using current versions of SAS/STAT and/or R packages lme4 and coxme, unless better packages become available in the meantime.

Further Planned Analyses

We note that there are other pre-specified outcomes intended for exploratory analysis in secondary papers for the INSPIRE ABD trial in Table 5 below.

Table 5: Secondary Manuscripts - Other Pre-Specified Outcomes

Secondary Manuscripts (other pre-specified secondary exploratory analyses for later manuscripts)	
Inpatient Extended-Spectrum Days of Therapy after the Empiric Period	The number of different ES antibiotics received each day, on hospital days ≥ 4 and ≤ 14 .
Empiric and Total Antibiotic Costs	Empiric and total antibiotic costs during hospitalization
Incidence of Hospital-Onset C. difficile	Hospital-onset C. difficile positive tests (specimen obtained) on hospital days ≥ 4 and ≤ 14 .
Incidence of Hospital-Onset MDRO-positive Cultures	Newly-detected hospital-onset MDRO-positive cultures on hospital days ≥ 4 and ≤ 14 . Includes total MDRO and specific MDRO subsets.

6. Moynihan R, et al. Impact of COVID-19 pandemic on utilisation of healthcare services: a systematic review. *BMJ Open* 2021;11:e045343. doi:10.1136/bmjopen-2020-045343.
7. Berkmeier, JD, et al. The Impact Of The COVID-19 Pandemic On Hospital Admissions In The United States. *Health Affairs* (39):11, September, 2020. <https://doi.org/10.1377/hlthaff.2020.00980>
8. Richmond BK, et al. The Impact of the COVID-19 Pandemic on Surgical Practice in the Southeastern United States: Results of a Survey of the Membership of the Southeastern Surgical Congress. *Am Surg.* 2020 Aug;86(8):916-925. doi: 10.1177/0003134820945203. Epub 2020 Sep 14.
9. Nguyen JL, et al. Pandemic-related declines in hospitalization for non-COVID-19-related illness in the United States from January through July 2020. *PLoS ONE* 17(1): e0262347. <https://doi.org/10.1371/journal.pone.0262347>.
